9. WHO Recommendations for the Prevention and Treatment of Postpartum Haemorrhage. Geneva: World Health Organization; 2012.
10. WOMAN Trial Collaborators. Effect of early tranexamic acid administration on mortality, hysterectomy, and other morbidities in women with post-partum haemorrhage (WOMAN): an international, randomised, double-blind, placebo-controlled trial. Lancet. 2017 Apr 26.

Research Design:

a. General Approach: Prospective Cohort study

b. Description: Phase 4

c. Methods: One Arm

d. Statistical Analysis:

- SPSS software will be used for our statistical analysis. Normal distribution will be assumed given the intended number of patients for analysis. Categorical variables will be analyzed using the Chi-square test. The t-test will be utilized for the comparison of continuous interval data.

-Using postpartum hemorrhage rate of 2.86% (institutional data), and a desired impact of reducing the hemorrhage rates by 50% after implementation of the new protocol, then 890 subjects would need to be recruited to answer the question.

e. Safety Analysis Plan:

- Data collection for each participant will occur in real time during pre and post delivery times, therefore safety monitoring of the patient and data will be simultaneous.
- A Research monitor has been appointed to oversee the safe and ethical conduct of the study. Additionally, the Research Monitor will provide review and comment on any adverse events. The Research Monitor is not a member of the investigative team. The role of the Research Monitor is as follows:
 1. monitor the consent process to ensure an absence of coercion
 2. monitor data collection/clinical outcome
 3. review all adverse event reports with comments from the PI and forward to the IRB with his/her own comments. Adverse events must be received by the IRB within 5 business days of occurrence or reporting (within 24 hours for serious adverse events)
 4. ensure the inclusion/exclusion criteria are followed
 5. review data security measures
- Any emerging safety concerns to include any adverse event rate higher than this institution's historical average will result in a halt to the study.

Subject Population:

Pregnant women presenting for delivery at NMCSO

a. Exclusion/Inclusion criteria:

Exclusion:

- a. Age less than 18 years
- b. Planned cesarean hysterectomy
- c. Current anticoagulant use
- d. Subarachnoid hemorrhage
- e. Any active/current intravascular clotting (i.e. venous thromboembolic events)

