- f. Patients with a hypersensitivity to TXA or any of the ingredients

- g. History of venous or arterial thrombotic events because use of tranexamic acid is a risk factor for thromboembolism.
- h. Conditions that predispose patients to thromboembolic events (e.g. thrombophilias, autoimmune diseases such as lupus, active cancer, congestive heart failure) because of increased risk of thrombosis
- i. Patients taking factor IX complex concentrates or anti-inhibitor coagulant concentrates (e.g. FEIBA NF)
- j. Seizure disorder because the use of tranexamic acid has been associated with postoperative seizures
- k. Patients with a baseline creatinine 1.2 or higher, history of renal insufficiency, or renal disease because of the risk of toxicity in patients with preexisting disease.
- l. Patients with frank hematuria because ureteral obstruction due to clot formation has been reported in patients with upper urinary tract bleeding who were treated with tranexamic acid
- m. History of retinal disease as cases of central retinal artery and vein obstruction have been reported in patients treated with tranexamic acid
- n. Patients with acquired defective color vision
- o. Patients with retinal diseases; cases of central retinal artery and central retinal vein obstruction have been reported in patients treated with intravenous tranexamic acid.

Inclusion:

-Pregnant women 18-54 years old delivering at Navy Medical Center San Diego (NMCS D)

Recruitment Process:

Patients will be identified in the antenatal clinics of Naval Medical Center San Diego. All patients that meet the inclusion criteria will be offered inclusion in the study.

All English speaking women who are eligible to receive care at NMCS D and presenting to NMCS D's Labor and Delivery Unit, who are at least 18 years old, not older than 54, and who are scheduled to deliver at NMCS D, will be given verbal and/or a written information sheet about the study and a description of what the study entails. OBGYN staff providers and residents will also be given an information sheet about the study. Opportunities for potential participant recruitment include:

- NMCS D Prenatal Registration
- NMCS D Gestational Diabetes education classes
- NMCS D Labor and Delivery tour of the unit

Subject eligibility and screening will take place prior to offering potential subjects the opportunity to participate in the study. An eligibility and screening tool will be used as part of the recruitment process.

Consent Process:

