Within this study, the use of protected health information (PHI) involves no more than a minimal risk to the privacy of individuals as there is a clear plan to protect the identifiers from improper use and disclosure. All identifiers will remain in the protected medical record and any identifier extracted will be destroyed at the earliest opportunity consistent with conduct of the research, unless there is a health or research justification for retaining the identifiers or such retention is otherwise required by law. PHI will not be reused or disclosed to any other person or entity, except as required by law, for authorized oversight of the research study, or for other research for which the use or disclosure of protected health information would be permitted by approval of the IRB.

We do not anticipate any risk to subjects participating in this study other than those encountered in routine labor and delivery experiences. TXA is being used in the hopes of reducing the amount of bleeding experienced in postpartum hemorrhage events. It will not eliminate all bleeding or need for a transfusion.

Risk/Side effects of TXA:

Contraindications

- Patients with subarachnoid hemorrhage. Anecdotal experience indicates that cerebral edema and cerebral infarction may be caused by TXA in such patients
- Patients with active intravascular clotting (e.g. venous thromboembolic events)
- Patients with hypersensitivity to TXA or any of the ingredients

Precautions

- The dose of TXA should be reduced in patients with renal insufficiency because of the risk of accumulation
- Patients with a previous history of thromboembolic disease may be at increased risk for venous or arterial thrombosis. More specifically, patients with DVT within one year, a hypercoagulable genetic disorder, a history of previous stroke, significant coronary artery disease, cardiac stents requiring ongoing clopidogrel (Plavix) treatment, or unstable angina are likely not appropriate candidates for TXA

Adverse Reactions

- Gastrointestinal disturbances (nausea, vomiting, diarrhea) may occur but disappear when the dosage is reduced
- Allergic dermatitis, giddiness, and hypotension have been reported occasionally
- Hypotension has been observed when intravenous injection is too rapid

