Rates of hysterectomy – the number of patients requiring hysterectomy divided by the total number of deliveries

Admission to the Intensive Care Unit (ICU) - the number of patients requiring admission to the intensive care unit secondary to excessive blood loss divided by the total number of deliveries

Neonatal outcomes – incidence of fetal anemia, infection, hyperbilirubinemia, neurologic outcomes, and neonatal intensive unit admissions

Maternal mortality – incidence of mortality

Additionally, postpartum hemorrhage risk assessment will be utilized to stratify patients with regard to primary and secondary outcomes.

- Patients will be risk stratified to one of three risk categories depending on admission and intrapartum risk factors
 - High Risk Factors:
 - Placenta previa/ low lying placenta
 - Suspected accreta or percreta
 - Platelet count <70,000
 - Active bleeding
 - Known coagulopathy
 - Two or more medium risk factors
 - Medium Risk Factors:
 - Prior cesarean delivery, uterine surgery, or multiple laparotomies
 - Multiple gestation
 - > 4 prior births
 - Prior obstetric hemorrhage
 - Large myomas
 - EFW >4000
 - BMI > 40
 - Hct < 30%
 - Chorioamnionitis
 - >24 hours on Oxytocin
 - Magnesium sulfate
 - Low Risk: all patients not falling in the medium or high risk categories

Importance to Navy Medicine:

Beyond the potential impact that this study has in the reduction of maternal morbidity and mortality, it can also allow for perspective into resource management. Some of the Navy Military Treatment Facilities (MTFs) have limited blood bank stock, and massive hemorrhages requiring ongoing transfusion of products can quickly deplete the entirety of the supply. If we can find a solution that will reduce the number of instances where transfusion is necessary we can help to preserve limited resources. Likewise, this preventive measure will also have the potential to (cost) reduce the need for additional uterotonics, personnel, supplies and ICU beds.

There will be no collaboration with outside institutions.

Supplement A: TXA Protocol Administration (Modified from the NMCS Maternal Child Executive Committee's Policy)

1. TXA comes in a 1000 mg/10 mL vial. Nursing staff will pull this from the Pyxis at the same time they bring Oxytocin into the L&D room.
2. Add 1000 mg (or 1 vial) of 1000 mg/10 mL to 100 mL normal saline (100 mg/mL)
 - a. Bolus: 1 gram IV over 10 minutes
 - i. Set infusion pump rate to 600 mL/hr

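### Three cardiac conditions, and part of the stroke history, that the protocol's own Precautions call likely unsuitable for TXA are not named in the exclusion criteria

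*Combined protocol and SAP*

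**What the plan says.** Two parts of the protocol describe who should not receive the drug.

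The first is the exclusion list under Subject Population, criteria a to o. Those that matter here are:

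- c: women currently on anticoagulants.
- d: "Subarachnoid hemorrhage".
- e: "Any active/current intravascular clotting (i.e. venous thromboembolic events".
- f: "Patients with a hypersensitivity to TXA or any of the ingredients".
- g: any past venous or arterial thrombotic event.
- h: conditions that predispose to thromboembolism, with thrombophilia, autoimmune disease, active cancer and heart failure as examples.
- k: raised creatinine or kidney disease.

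The second is Risk/Side effects of TXA, in the Risks section. Its Contraindications are subarachnoid hemorrhage, active clotting ("Patients with active intravascular clotting (e.g. venous thromboembolic events") and hypersensitivity. Its Precautions advise on renal insufficiency. They then name deep vein thrombosis in the past year, a genetic clotting disorder, past stroke and significant coronary artery disease, and close with "cardiac stents requiring ongoing clopidogrel (Plavix) treatment, or unstable angina are likely not appropriate candidates for TXA".

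Recruitment Process says that an eligibility and screening tool will be used. Justification/Minimization of Risks says that the institutional TXA policy will be followed. The content of the tool and the full policy are not in the document.

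**The concern.** Every enrolled woman is to receive TXA preventively, including those at low risk of hemorrhage. The exclusion list is therefore the main written barrier between the drug and a woman whom the Risks section considers a poor candidate. If a condition appears in the Precautions but not in the exclusions, a screener who follows the listed criteria can enrol her, and two careful screeners can reach different decisions.

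The later steps do not obviously catch the omission. Under Study Procedures, the steps on Labor and Delivery re-identify the participant and go on to order the drug, with no listed re-check of eligibility. The Research Monitor is asked to ensure that the inclusion and exclusion criteria are followed, which means checking against the same list.

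The stake is mainly the safety of a few women. There is also a possible effect on study conduct. The Safety Analysis Plan halts the study if any adverse event rate exceeds the institution's historical average, so an avoidable event in a woman the protocol itself considers unsuitable could count towards a halt. No sample size, error rate or estimate depends on this point.

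**Working it through.** No formula applies. The check sets each item in the Risks section against exclusions a to o.

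**Contraindications (three)**

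| Contraindication | Exclusion | Result |
|---|---|---|
| "Patients with subarachnoid hemorrhage. Anecdotal experience indicates that cerebral edema and cerebral infarction may be caused by TXA in such patients" | d | Covered |
| "Patients with active intravascular clotting (e.g. venous thromboembolic events" | e | Covered; *i.e.* in e, *e.g.* here |
| "Patients with hypersensitivity to TXA or any of the ingredients" | f | Covered |

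Result: 3 of 3 have a matching exclusion, one with a difference in wording.

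**Precaution conditions (seven)**

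| Condition | Exclusion that reaches it | Result |
|---|---|---|
| Renal insufficiency | k, which excludes outright where the Precautions speak of a reduced dose | Covered |
| Deep vein thrombosis within a year | g, with no time limit | Covered, more strictly |
| Genetic hypercoagulability | h, through thrombophilias | Covered |
| Past stroke | g if thrombotic; d if subarachnoid hemorrhage; otherwise none by name | Partly covered |
| Significant coronary artery disease | None by name | Not named |
| Cardiac stent with continuing clopidogrel | None by name | Not named |
| Unstable angina | None by name | Not named |

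Count: 3 covered + 1 partly covered + 3 not named = 7.

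**Could another criterion close the gap for the last four rows?**

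- Criterion c names anticoagulants. Clopidogrel is an antiplatelet drug, so a woman with a stent is not caught by c as written.
- Criterion g needs a thrombotic event. Coronary disease or angina without such an event falls outside it, as does a non-thrombotic stroke.
- Criterion h is open-ended, so a screener may read the cardiac conditions into it. Its only cardiac example is heart failure, and nothing tells the screener that coronary disease, a stent or angina belongs there.

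Coverage of the three cardiac conditions therefore depends on how each screener reads h, or on the woman also having a thrombotic history under g.

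**The case against.** The strongest reply is that h already covers the cardiac conditions. The Precautions introduce them as specific instances, straight after a statement about the risk of venous or arterial thrombosis, so the document itself treats them as thrombosis-risk conditions. Leaving a condition out of a list of examples does not leave it out of the criterion. This is a reasonable reading, and it stands as one. It does not remove the need for a clear rule, because h does not say so and a screener could equally well read it the other way.

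A second reply is that other safeguards exist. The screening tool may already ask these questions, the institutional policy is to be followed, the investigator may end participation judged harmful, and the Research Monitor may remove participants. All of that is possible. But the content of the tool and the full policy cannot be seen, so neither can be assumed to fill the gap. The other two are general powers and do not settle eligibility for these conditions.

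A third reply is that the conditions are precautions, not contraindications, and are rare in this population. Both parts are fair, and they limit the weight of the point. The document nevertheless calls these women likely unsuitable, and a trial giving the drug preventively should say whether it enrols them.

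A reader might also infer more than the documents support:

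- *That contraindicated women pass screening.* Each contraindication has its own exclusion. The *i.e.* in e sits under a head phrase that takes in any active or current intravascular clotting, so the difference from *e.g.* is a matter of wording.
- *That the exclusion list as a whole is narrower than the Risks section.* On most items it is equal or wider. It adds lupus, active cancer, heart failure, seizure disorder, frank hematuria, retinal disease and others.
- *That the high-risk factor "Known coagulopathy" admits women with active consumptive clotting.* That list classifies hemorrhage risk for the analysis. It grants no eligibility and overrides no exclusion, and the documents do not mention disseminated intravascular coagulation or abruption.
- *That screeners would disagree about an old deep vein thrombosis.* Criterion g excludes any thrombotic history, so they would not. The one-year window is part of a statement on drug risk, and a trial may exclude more than a precaution requires.

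**Conclusion.** The point holds in a limited form. Three of the seven precaution conditions (significant coronary artery disease, a stent with continuing clopidogrel, unstable angina) are named in no exclusion. A fourth, past stroke, is only partly covered, because non-thrombotic stroke other than subarachnoid hemorrhage is not reached. The written criteria can therefore admit women whom the same document calls likely unsuitable, unless a screener reads h broadly.

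The number of women cannot be computed, since the documents give no prevalence. For scale only, an assumed frequency of 0.1% to 0.5% would mean 890 × 0.001 = 0.9 to 890 × 0.005 = 4.5 women, less those whom g or h already excludes. Nothing in the documents supports that range, and the conclusion does not rest on it.

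The conclusion assumes that screeners work from the listed criteria and that the unseen tool and policy do not already settle these conditions. The correction should be made because the possible harm is serious and the remedy is nearly free. It does not call the design or the analysis into question.

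**What to change.** Reconcile the exclusion criteria under Subject Population with the Precautions under Risk/Side effects of TXA. For each of the four conditions (past stroke, significant coronary artery disease, stent with continuing clopidogrel, unstable angina) the clinical leads should decide whether it is an exclusion. The criteria and the eligibility tool should then state that decision explicitly, with a yes/no item in the tool for each. Which way each decision goes is a clinical matter and is not proposed here.

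In the same edit, align the *i.e.* in criterion e with the *e.g.* in the Contraindications, as a change of wording only.

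The cost is a protocol wording change, a few extra checklist items and possibly a very small number of women becoming ineligible. If the tool or the institutional policy already covers these conditions, the change only brings the protocol text into line with practice.

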 2. For patients that present for delivery at a gestational age less than 34 weeks, it will be recommended that they discard their breast milk until 24 hours after their last TXA administration.
 3. Order TXA for patient in ESSENTRIS
 4. RN to pull TXA from Pyxis and put in patient's room
 5. TXA per protocol (see supplement A)
 6. The use of additional uterotonics or single additional dose of TXA is at the discretion of the delivering provider
 7. For patient monitoring protocol please see Supplement B.
 8. All neonates are monitored for a minimum of 24 hours either by the NICU or the Newborn Nursery. Vitals are taken every four hours. Weights and bilirubin levels are obtained daily. Daily physical exams are performed.
3. Data collection
 1. Participants will be assigned an individualized subject number upon their enrollment to the study.
 2. Participants will be followed from their enrollment into the study until six weeks postpartum.
 3. An Excel spreadsheet will be used to collect the variables as listed above.
 4. Once the variable collection is complete, the information will become de-identified.

5. Chart review will be performed to estimate institutional rates of the secondary outcomes in the 12 months preceding the initiation of the protocol.
4. Data Analysis
 1. SPSS software will be used for our statistical analysis. Normal distribution will be assumed given the intended number of patients for analysis. Categorical variables will be analyzed using the Chi-square test. The t-test will be utilized for the comparison of continuous interval data.
 2. Using a postpartum hemorrhage rate of 2.86% (institutional data), and a desired impact of reducing the hemorrhage rates by 50% after implementation of the new protocol, then 890 subjects would need to be recruited to answer the question.
 3. The secondary outcomes will also be tested against institutional rates. Institutional rates will be estimated by record sampling done at the time of data collection.

Experimental Procedures:

See supplement A

Research materials collected:

Variables to be collected:

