Age, race/ethnicity, DoD status, BMI, gestational age, # of fetuses, gravidity, parity, admission diagnoses, admission estimated fetal weight, intrapartum diagnoses, postpartum diagnoses, misoprostol use, oxytocin use, mechanical dilation, duration of labor, magnesium sulfate use, planned mode of delivery, mode of delivery, birth weight, indication for operative delivery, neonatal outcomes, maternal outcomes, admission to the intensive care unit, uterotonic use, mechanical tamponade, blood product transfusion, estimated blood loss, qualitative blood loss, cumulative blood loss, laboratory results, post-delivery laboratory results

Confounding variables:

Management of the 3rd stage of labor

Source of the data:

Outpatient records (AHLTA), Inpatient records (Essentris). As providers, the investigators have access to these systems as a standard of care for patients receiving care from investigator-providers.

Paper records created in the Labor and Delivery department during the course of a delivery.

The data collected will be measured against the historic PPH rates of NMCSO over a period of time to be determined.

Protection of Privacy:

Each participant will be given a unique study number. A master list with only the minimal Personal Identifiable Information (PII) needed for follow up and their study number will be kept in the PI's office on a CAC PIN protected computer in the PI's locked office. The master list will be used to track the results of the study participant's data collection.

An Excel spread sheet will be used to collect this information using only the participants unique study number and stored electronically on a CAC PIN protected computer in the PI's locked office.

All data and PII will be destroyed (shred or deleted) at the conclusion of this project.

Risks:

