- Rare events from worldwide post marketing reports have included thromboembolic events (e.g., deep vein thrombosis, pulmonary embolism, cerebral thrombosis, acute renal cortical necrosis, and central retinal artery and vein obstruction), convulsion, chromatopsia, and visual impairment

Radiation/Laser Exposure: None

Justification/Minimization of Risks:

All identifiers will remain in the protected medical record. Any PHI extracted as a result of this study will be destroyed at the earliest opportunity consistent with conduct of the research, unless there is a health or research justification for retaining the identifiers or such retention is otherwise required by law. Protected health information will not be reused or disclosed to any other person or entity, except as required by law, for authorized oversight of the research study, or for other research for which the use or disclosure of protected health information would be permitted by approval of the IRB.

The current Maternal Child Executive Committee Policy on Tranexamic Acid (TXA) Administration will be followed to minimize any risks of harm to subjects.

Benefits:

Potential benefits of the research to the subject include a reduction in blood loss from delivery, decreased need for uterotonic medications, decreased need for blood transfusion, and less morbidity as a result of symptomatic anemia, resulting in increased satisfaction with the postpartum experience and increased maternal-neonate interactions.

Potential benefits of the research to the community/society included less overall maternal morbidity/mortality as well as a decreased demand on limited resources (i.e. blood products, uterotonic medications, time of additional healthcare providers, etc).

Requirements for Research Monitor:

Research Monitor Responsibilities:

Serves as a medical monitor, reviewing AEs as they are discovered to determine if the events suggest a trend toward increased risk to subjects that would require additional safeguards, subject notifications, or an invoking of stopping rules.

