3. Begin the TXA infusion directly following umbilical cord clamping for the intent of preventing postpartum hemorrhage.
 - a. The TXA may be run as a secondary line (i.e. is compatible with pitocin) per [name], Chairman of the Pharmacy Department
4. TXA should be administered in a separate IV line from blood products.
5. Two-person verification is required (this can be a second nurse or can be the physician or certified nurse midwife that is attending the delivery)
6. A single additional dose of TXA (1 gram IV over 10 minutes) can be repeated after 30 minutes if bleeding continues or if bleeding stops and then re-starts within 24 hours of the first dose (for a maximum dose of 2g in 24 hours). This additional dose is considered a treatment dose. This additional dose is not required by the study design, which is to assess TXA in the *prevention* of hemorrhage.

Supplement B: Patient Monitoring following delivery

1. After delivery patients will be observed on the Labor and Delivery floor for a minimum of one hour. Thereafter they will be transferred to the postpartum ward where they will be observed for a minimum of 24 hours.
2. The following physical assessments will be completed every 15 minutes x 1 hour , then every 30 min x 2 hours, then every 4 hours until discharge.
 - A. Vital signs: BP and pulse as above. Temperature Q1 hour (after 2 normal values will space to Q4 hours).
 - B. Fundal assessment: Placement and tone
 - C. Lochia assessment: Color, with or without clots, amount
 - D. Perineum assessment: Intactness (approximation of tissues/wound/lacerations), hematomas, swelling
 - E. Bladder assessment: Distention, voiding (noting/documentation of most recent void/amount, spontaneous/catheterization).
 - F. Any symptoms that the patient reports.
3. The nursing staff will immediately report any findings that are not within normal limits to the delivering provider or on-call provider:
 - A. BP systolic > 160 or < 100
 - B. BP diastolic > 90 or <50
 - C. Pulse > 100
 - D. Nausea, dizziness or SOB
 - E. Moderate to copious lochia
 - F. Increased swelling or pain in vagina or perineal/rectal area
 - G. Distended bladder not relieved by catheterization or patient voiding
 - H. Fundus displaced or above umbilicus (if differs from initial normal placement of uterus), unrelieved with empty bladder.
4. Documentation
 - A. All assessments are documented in Essentris. See below for notes needed:
 - B. Complete intake and output flow sheet

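### Follow-up is stated to six weeks, but after discharge harms are found only passively, and TXA's named risks are neither listed outcomes nor given a historical baseline

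*Combined protocol and SAP*

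**What the plan says.** **Follow-up.** Study Procedures, Data collection item 2: "Participants will be followed from their enrollment into the study until six weeks postpartum". No visit, call, questionnaire or dated record review is assigned to the weeks after discharge.

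**Scheduled assessment.** Supplement B item 2 sets maternal checks at decreasing frequency, "then every 4 hours until discharge". The minimum stay is one hour on Labor and Delivery plus 24 hours on the postpartum ward. For newborns, "All neonates are monitored for a minimum of 24 hours either by the NICU or the Newborn Nursery". The Safety Analysis Plan says "Data collection for each participant will occur in real time during pre and post delivery times" and gives no end to the post-delivery part.

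**Named risks.** The adverse reactions list states: "Rare events from worldwide post marketing reports have included thromboembolic events". Its examples include renal cortical necrosis and retinal vessel obstruction, and it goes on to convulsion and disturbed vision. Exclusions e, g, h, j, k, m, n and o concern clotting, seizure, renal, retinal or color-vision conditions.

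**Listed outcomes.** Apart from bleeding and its consequences, the only maternal outcome is "Maternal mortality – incidence of mortality". The intensive care outcome counts "the number of patients requiring admission to the intensive care unit secondary to excessive blood loss".

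**Other routes to an event.** The variables list includes "intrapartum diagnoses, postpartum diagnoses, misoprostol use", maternal outcomes, laboratory results, and intensive care admission without restriction by cause. Sources include outpatient (AHLTA) and inpatient (Essentris) records. Adverse events must reach the IRB within 5 business days, or 24 hours if serious, and the Research Monitor reviews them.

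**Baseline and halt rule.** Data collection item 5 plans a chart review of secondary-outcome rates over the 12 months before the protocol starts. The Safety Analysis Plan halts the study if any adverse event rate exceeds the institution's historical average. It gives no event list, rate or time window.

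**The concern.** TXA is given here as prevention at delivery to women who mostly would not hemorrhage, so any benefit has to be weighed against its recognized harms. The plan names those harms at length when it screens women out, but does not name them among the things it will count. The six-week follow-up statement invites the reader to take an absence of reported thrombosis as evidence over six weeks. The plan does not say how a woman's status over that period becomes known.

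The halt rule has the same difficulty. It needs a study rate and a historical rate for each adverse event. For thrombosis, seizure, visual and renal events the plan describes no systematic collection of the first and no planned estimate of the second.

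The gap may be hard to close later. The data are de-identified once variable collection is complete, and data and identifiers are destroyed when the project ends.

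**Working it through.** **1. What the 890 was sized for.** Inputs from Research Design, Statistical Analysis: p0 = 0.0286, a 50% reduction, hence p1 = 0.0143. Alpha, sidedness and power are not stated. Assuming a one-sample test against a fixed rate, two-sided 5% and 80% power:

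n = [(1.960 × √(0.0286 × 0.9714) + 0.842 × √(0.0143 × 0.9857)) / 0.0143]² = 890.0

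The plan's figure is reproduced. One-sided 5% with 90% power gives 888.8, so the text does not settle which was used. Either way the number concerns hemorrhage only; no safety event enters it.

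**2. Named risks against planned capture.**

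| Named risk | Listed outcome? | Scheduled maternal check after discharge? | Historical rate planned? |
|---|---|---|---|
| Venous or arterial thromboembolism | No | No | No |
| Seizure | No | No | No |
| Visual disturbance | No | No | No |
| Renal injury | No | No | No |

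The last column follows from the second: the chart review is limited to secondary outcomes, and none of these events is one. An intensive care admission for pulmonary embolism would fall outside the intensive care outcome, though it could appear in the unrestricted variable.

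**3. What zero recorded events would show.** With complete capture in n = 890, the exact one-sided 95% upper limit for the true rate is

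1 − 0.05^(1/890) = 0.336%.

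If only a fraction c of events is captured, the chance of recording none is (1 − c × p)^890. Setting this to 0.05 gives p = 0.336% / c. The documents give no value for c, so it is shown over an assumed range:

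| Assumed capture c | Upper limit for true rate |
|---|---|
| 100% | 0.34% |
| 75% | 0.336 / 0.75 = 0.45% |
| 50% | 0.336 / 0.50 = 0.67% |
| 25% | 0.336 / 0.25 = 1.34% |

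**4. How often zero would be seen.** P(none recorded) = (1 − c × p)^890 for two assumed true rates:

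| True rate (assumed) | Expected events in 890 | c = 100% | c = 50% | c = 25% |
|---|---|---|---|---|
| 0.1% | 0.89 | 41% | 64% | 80% |
| 0.2% | 1.78 | 17% | 41% | 64% |

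Incomplete capture makes a clean safety result much more likely without any change in the true rate.

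**The case against.** The best defense is that the plan does have ways to find these events. Outpatient records cover the weeks after discharge. The fields for postpartum diagnoses and maternal outcomes could hold a thrombosis. Study participation is flagged on the hard chart and in the electronic record templates, and the master list keeps identifiers for follow-up. Symptoms are recorded on the ward, where shortness of breath and dizziness must be reported. The Research Monitor oversees data collection and may interview participants. The stated aim is efficacy, and the plan announces no conclusion about harm to six weeks. Most of this stands, and it rules out several stronger readings that a reader might infer:

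- *That the study does not look for harm, or that the Research Monitor sees nothing after discharge.* The routes above exist. They are passive and undefined, which is a lesser fault.
- *That an unseen event will be counted as no event.* The plan does not say how unknown status is coded.
- *That the data sheet has no place for these events.* The attached spreadsheet is not in the public document, so its fields cannot be held against the plan.
- *That only the first of 42 days (1/42 = 2.4%) is covered.* That counts scheduled bedside checks at the minimum stay and ignores the records.
- *That half of all events would be missed.* No capture rate is given; 50% is one assumed value in a range.

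It is also fair to say that 890 women are too few to rule out a rare harm: even with full capture, a true rate of 0.1% yields no events 41% of the time. And questioning only treated women, then comparing them with chart-based history, would bias the comparison against TXA and could trip the halt rule through better detection alone. Both points shape the remedy.

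The defense does not answer the mismatch within the plan itself: a stated six-week window with no described way to establish status in it, and a halt rule that refers to historical rates not planned for the drug's main named risks.

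**Conclusion.** The point holds as a gap in how safety is ascertained, and it should be fixed. After discharge, detection of the named risks is passive and unspecified. None of them is a listed outcome, and so none has a planned historical rate for the halt rule to use. The follow-up statement, the outcome list, the chart review and the halt rule need to be reconciled.

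A finding of no safety signal would be weakly supported. Zero events in 890 women would exclude true rates above 0.34% only if capture were complete; over the assumed range of 75% to 25% capture the limit runs from 0.45% to 1.34%. These figures assume 890 treated women, no recorded events, and the same chance of capture for each event. The hemorrhage sample size is unaffected.

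**What to change.** 1. **Secondary outcomes:** add maternal venous or arterial thromboembolism, seizure, new visual disturbance and acute renal injury, from TXA administration to six weeks postpartum, as secondary safety outcomes with a short definition of each. The historical chart review then covers them under its existing wording.
2. **Data collection items 2 and 5:** abstract these events from the same outpatient and inpatient records, over the same six weeks after delivery, for study women and for the 12-month historical review. Report the number of historical records examined with each rate.
3. **Denominator:** record for each woman whether her six-week status is known. Report event rates with exact confidence limits on that denominator, and state how many women have unknown status.
4. **Optional contact:** ask about these events and about care received elsewhere, at a routine postpartum visit or by a short call. Report events found only this way separately and leave them out of the historical comparison, because the historical women had no such contact.
5. **If six-week status is not ascertained:** limit any safety statement to the period and sources actually covered.

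The cost is a few more data fields, more chart abstraction in both periods, and probably a few more recorded events. If the optional contact is adopted, it adds staff time for each woman. None of this changes treatment or the 890, and it does not make the study large enough to exclude a rare harm; it makes the limit that is reported an honest one.
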